Statistical Methodology	
The primary efficacy analysis for temperature maintenance will be based on the evaluable population of subjects who achieve normothermia by 4 hours and continue cooling treatment with the COOLSTAT System.
 
The proportion of subjects fulfilling success criteria and 90% confidence intervals will be reported and compared to the a priori minimum acceptable criteria:
 
 • at least 75% of the subjects will reach normothermia (core temperature $\leq 37.5^{\circ}\text{C}$) within 4 hours of starting COOLSTAT cooling, and • at least 75% of the subjects' core temperatures remain between 36°C and 37.5°C for 80% of the steady state time following the initial achievement of 37.5°C. 
All adverse events (AEs) reported during the study will be presented in tabular format to include: time of onset, whether or not the patient continued in the study, the nature of intervention and resolution. The potential contribution to the AE by the device will be assessed by the attending physician who reports the AE and the investigator.

Data Safety Monitoring Board	
A DSMB will be formed to monitor this study. The DSMB will meet: 1) before any subjects are enrolled (to review the study), 2) after the first 5 subjects (all with ICP monitoring), 3) after the first 10 subjects (before proceeding to 24-hour

upon being reconnected to the CoolStat is $\leq 37.5^{\circ}\text{C}$. If the subject's temperature is $> 37.5^{\circ}\text{C}$ upon being reconnected to the device, the device will be given up to an additional 4 hour-period to bring the patient to normothermia ($\leq 37.5^{\circ}\text{C}$). Once the subject's core temperature is $\leq 37.5^{\circ}\text{C}$, the device will be considered in steady state.

cooling treatment), 4) after each 6-month period of study, 5) at the end of the study, and 6) after any serious adverse event.

A clinical monitor will also be used to periodically visit the study sites and monitor the activities of the study to ensure that the study protocol, consent activities and data collection are being completed in accordance with specified procedures.

The Clinical Monitor and DSMB will be comprised of:

- [name] - Clinical Monitor
- [name] (Johns Hopkins) - Chair of DSMB - Voting Member
- [name] (Johns Hopkins) - DSMB Voting Member
- [name] (UMMC) - DSMB Voting Member
- [name] (UMMC) - DSMB Voting Member
- [name] (UMMC) - PI (Non-Voting Member)

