Similarly, per standard of care in the NCCU, a maximum allowed limit will be imposed for a sustained increase in ICP >5 minutes above max threshold despite standard of care intervention (using existing max institutional limits for the indication being treated). In this event, COOLSTAT use will be discontinued for that subject. Once the COOLSTAT is discontinued due to ICP elevation, it will not be restarted for that subject. However, the study team will continue to monitor ICP to see if it recovers back to baseline value after the COOLSTAT is turned off. The Investigator or their designee must complete an Adverse Event form detailing the event and the value of the ICP prior to, during and after the COOLSTAT was used. See Section 10.0 on procedures following the occurrence of an Adverse Event.

The Investigator or their designee will perform an initial cooling assessment 4 hours after COOLSTAT cooling has begun to determine if the subject has reached normothermia (≤ 37.5 C) sometime within the 4-hour cooling period. Starting from the initiation of normothermia, a subject's core temperature may fluctuate (within about 36.0-37.5 C), but

Transnasal Induction of Normotherapy in NCCU Fever Patients

if the core temperature $>39.0^{\circ}\text{C}$ for 4 hours, CoolStat treatment will be stopped and the subject will be switched to an alternative cooling method. If normothermia ($\leq 37.5^{\circ}\text{C}$) is not achieved within the 4-hour period, the Investigator or their designee will remove the subject from the COOLSTAT device. The subject will be classified as a treatment failure and placed on standard of care treatment at the discretion of the Investigator or their designee and manual data collection will continue per the instructions for Phase 2 in Section 9.4. NOTE – if the Investigator feels that the subject's temperature is approaching the target and the subject is being adequately cooled, CoolStat device operation can be allowed to continue beyond the 4-hour period. The Investigator should note if this is the case in the CRF.

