If a subject must be disconnected from the CoolStat device for transport from the NCCU to another unit (e.g., to radiology or angiography suite), they will be reconnected to the device at steady state if their core temperature upon being reconnected to the CoolStat is $\leq 37.5^{\circ}\text{C}$. If the subject's temperature is $> 37.5^{\circ}\text{C}$ upon being reconnected to the device, the device will be given up to an additional 4 hour-period to bring the patient to normothermia ($\leq 37.5^{\circ}\text{C}$). Once the subject's core temperature is $\leq 37.5^{\circ}\text{C}$, the device will be considered in steady state. Only the total steady state time will be used for analysis. Subjects who are disconnected from the CoolStat for transport may be given a bolus of cold saline before transport. This will be determined by the clinical provider a case-by-case basis.

The COOLSTAT does not have a re-warming function. If the subject's core temperature drops below 36°C , warming therapies can be initiated at the discretion of the Investigator or the attending clinician(s). The subject can stay on the COOLSTAT and continue with the study as long as core temperature can be adequately controlled at the discretion of the Investigator or the attending clinician(s). Any change to therapy must be recorded in the case report form. COOLSTAT therapy will be discontinued if tympanic temperature drops below 34°C for a sustained period of at least 5 minutes.

The CoolStat nasal mask will be removed at least every 4 hours to inspect nasal tissue for the development of any pressure sores. Petroleum gel may be applied to facilitate a strong seal below the nasal mask pillows and the nostrils without requiring much pressure from the mask straps.

The COOLSTAT therapy will be discontinued at the end of Phase 1, at which point the subject can be placed on alternate cooling therapies at the discretion of the attending clinician.

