13.0 Statistical Analysis Plan

The primary efficacy analysis for cooling performance will be based on the evaluable populations of subjects who undergo cooling treatment with the COOLSTAT System. Analysis will be performed on treatment initiated and treatment completed populations. Subjects who achieve normothermia (core temperature $\leq 37.5^{\circ}\text{C}$) within 4 hours of starting COOLSTAT treatment and maintain normothermia for the duration of the treatment will be determined to have been treated successfully.

The primary efficacy analysis for temperature maintenance will be based on the evaluable population of subjects who maintain normothermia (core temperature between 36°C and 37.5°C) for at least 80% of the time following the initial achievement of 37°C will be determined to have been treated successfully.

The proportion of subjects fulfilling success criteria and 90% confidence intervals will be reported and compared to the a priori minimum acceptable criteria:

- at least 75% of the subjects will reach normothermia (core temperature $\leq 37.5^{\circ}\text{C}$) within 4 hours of starting COOLSTAT cooling, and
- at least 75% of the subjects' core temperatures remain between 36°C and 37.5°C for 80% of the steady state time following the initial achievement of 37.5°C .

Continuous measurements will be summarized using the mean and standard deviation. Categorical variables will be reported using percentages and confidence intervals. Data collected will be plotted to demonstrate the change in core temperature from baseline.

An exploratory analysis of participant subgroups will be performed, stratified by stroke presentation (ischemic versus hemorrhagic). Cooling performance and AEs will be evaluated by subgroup.

Double nostril air flow and single nostril air flow subjects will not be merged or directly compared. The results from subjects treated with single nostril flow will be analyzed separately from subjects treated with double nostril air flow.

Subjects 1 through 20 will be assigned to the double nostril air flow treatment group:

- Subjects 1 through 10 will be treated for 8 hours (N=10)
- Subjects 11 through 20 will be treated for 24 hours (N=10)

Subjects 21 through 30 will be assigned to the single nostril air flow treatment group

- Subjects 21 through 30 will be treated for 24 hours (N=10).
- Subjects 21 through 30 will be treated using a dose escalation model:
 - Dosing for this cohort (flow rate) will begin at 30 LPM.

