13.1 Primary Performance Outcome Analysis

The primary hypothesis regarding cooling performance is that at least 75% of the subjects will reach normothermia (core temperature $\leq 37.5^{\circ}\text{C}$) within 4 hours of starting COOLSTAT cooling.

The primary hypothesis regarding temperature maintenance is that at least 75% of the subjects' core temperatures remain between 36 °C and 37.5 °C for 80% of the steady state time following the initial achievement of 37.5 C.

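### A subject not re-cooled after a transport break has no maintenance score in the plan, and the steady-state denominator lets that subject pass on pre-transport hours alone

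*Combined protocol and SAP*

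**What the plan says.** Section 9.3, and the footnote to the hypotheses in section 1.0, deal with a subject disconnected for transport. If core temperature at reconnection is above 37.5 °C, "the device will be given up to an additional 4 hour-period to bring the patient to normothermia". Once it is 37.5 °C or lower, "the device will be considered in steady state". Section 9.3 then states: "Only the total steady state time will be used for analysis".

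The maintenance criterion in section 13.1 requires the 36–37.5 °C band "for 80% of the steady state time following the initial achievement of" 37.5 °C. The same steady-state wording appears in section 1.0 (Hypothesis, Outcomes and Statistical Methodology), section 6.3, the section 6.10 gate and the bullets of section 13.0.

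Three other statements do not fit it:

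- Section 13.0, second paragraph, asks for the band "for at least 80% of the time following the initial achievement of" 37 °C. It does not limit this to steady state and starts from a different temperature.
- Section 13.0, first paragraph, says that subjects who reach normothermia within 4 hours and "maintain normothermia for the duration of the treatment will be determined to have been treated successfully".
- Section 1.0 (Statistical Methodology) bases the maintenance analysis on the "evaluable population of subjects who achieve normothermia by 4 hours and continue cooling treatment with the COOLSTAT System".

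No section says how a subject who is not back at 37.5 °C or below within the extra window is scored for maintenance.

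**The concern.** Whether an hour on the device enters the denominator depends on whether the device has brought the temperature back down. That makes the denominator depend on the outcome. When re-cooling fails, the failed hours never become steady-state time, so the ratio rests only on the hours before transport, when the subject was doing well.

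Two decisions use this ratio. One is the 75% maintenance hypothesis. The other is the section 6.10 gate, which needs 8 of the first 10 subjects to meet the maintenance criterion before the move to 24-hour cooling. Section 13.0 also analyses the double-nostril group (subjects 1 to 20) separately, so a single subject carries weight. Because the sections point to different scores for the same subject, the choice between them could be made after the data are seen.

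**Working it through.** **Plan's own figures.** The gate reproduces: 75% of 10 is 7.5, so 8 of 10. The sample size also reproduces: [(1.28 × √(0.9 × 0.1) + 0.84 × √(0.75 × 0.25)) / 0.15]² = 24.85, so 25. Neither depends on the denominator rule; what changes is how a subject is classified.

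**Inputs from the documents.** Band 36–37.5 °C; threshold 80%; extra window up to 4 h; courses of 8 h (subjects 1–10) and 24 h (subjects 11–20). The documents give no transport times, so the hours below are assumed.

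**Formulas.** Plan's rule: in-band hours / steady-state hours. Alternative: in-band hours / (steady-state hours + on-device hours above 37.5 °C between reconnection and return).

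| Assumed course after first reaching 37.5 °C | Plan's rule | All on-device time |
|---|---|---|
| 1 h in band, transport, 4 h not re-cooled | 1/1 = 100% | 1/5 = 20% |
| 6 h in band, transport, 4 h not re-cooled | 6/6 = 100% | 6/10 = 60% |
| 14 h in band and 2 h out of band in steady state, plus 4 h re-cooling that succeeds | 14/16 = 87.5% | 14/20 = 70% |

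The first row fits an 8-hour course (for example 2 h to cool, 1 h in band, 1 h transport, 4 h on the device). The second needs the 24-hour course. The third subject was re-cooled and illustrates only the choice of denominator, not the missing score.

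**How much good time would offset a failed window?** x/(x + 4) ≥ 0.80 gives x ≥ 16 h, all in band. In an 8-hour course a full 4-hour window leaves at most 4 h, so at most 4/8 = 50%.

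**The 6 h + 4 h subject under each statement.**

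- Steady-state wording (sections 1.0, 6.3, 6.10, 13.1 and the 13.0 bullets): 100%, pass.
- Section 1.0 population, if the subject comes off the device after the window: possibly not in the denominator of subjects.
- Section 13.0, 80% of the time after 37 °C: at most 60%, because the later start removes only in-band time; fail.
- Section 13.0, normothermia throughout treatment: fail.

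**Effect on counts.** Take ten subjects: seven clear successes, two clear failures and one such subject. Scored as a failure, 7/10 = 70%. Scored as a success, 8/10 = 80%, and this part of the gate is met. Dropped, 7/9 = 77.8%, which exceeds 75%, although section 6.10 counts out of ten and does not say what to do with nine. In the double-nostril group one subject moves the rate by 1/20 = 5 points, or more if fewer than 20 are in the maintenance population.

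**Trial level, illustration only.** P(at least 8 of 10) = Σ C(10,k) pᵏ(1 − p)¹⁰⁻ᵏ for k = 8 to 10. Assume a true maintenance rate of 65%. If 0, 5, 10, 15 or 20% of subjects are reclassified as successes, this is 0.26, 0.38, 0.53, 0.68 or 0.82.

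**The case against.** The transport allowance is deliberate. It stands in a footnote to the primary hypotheses, and the revision table (Rev P5) records that the hypothesis and statistical plan were clarified for clinically required transport. Drift while off the device is not a maintenance failure of the device, and leaving out the re-cooling ramp mirrors the first ramp, which is also outside the maintenance period. All of this stands, and the allowance should stay. It does not settle the score of a subject for whom the ramp never ends.

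Section 5.5.1 says an internal battery allows cooling during short transports, so disconnections may be few. Section 6.8 calls the study exploratory. Both limit the weight of the point.

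Four stronger readings are tempting, and the documents do not support them.

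- *The plan declares such a subject a success.* It does not. The pass follows from the steady-state wording combined with a missing rule, and other sentences would fail or drop the subject.
- *The plan is stricter at first cooling than after transport.* The rule that "The subject will be classified as a treatment failure and placed on standard of care treatment" belongs to the assessment 4 hours after cooling began, hence to the cooling-performance endpoint, and section 9.3 lets the investigator continue beyond 4 hours. Under section 1.0 a subject who misses the first window is outside the maintenance population, so is not a maintenance failure either.
- *All fever after transport is excused.* Only the interval from reconnection to the first return is excluded; later time above 37.5 °C counts against the subject.
- *The failure vanishes from the study.* It drops out of one ratio. Core temperature is logged every second (section 12.6), insufficient cooling is a listed anticipated adverse event (section 10.4), and the close-out report covers all data collected (section 14.5).

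**Conclusion.** The point holds in this form: the maintenance score of a subject not re-cooled after transport is unspecified, the texts that bear on it conflict, and the wording used most often gives a pass based on pre-transport hours. Two of the three possible outcomes, pass and exclusion, favour the device in a primary endpoint. For an affected subject the difference is large: 100% against 60% or 20% in the assumed cases. At the gate one subject can decide between 7/10 and 8/10.

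The effect on the trial result cannot be sized. It needs a disconnection, a reconnection above 37.5 °C, failure to re-cool, and at least 80% in band beforehand, and the documents give no frequency for any of these. The probabilities above rest on assumed rates. A reader might infer that the maintenance rate will be materially inflated; the documents support only that it could be, and in which direction. This is a cheap improvement rather than a flaw that undermines the study.

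**What to change.** Analysis text only:

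1. Keep the transport allowance in the main analysis.
2. State in section 13.0 that a subject who first reached normothermia but is not back at 37.5 °C or below within the extra window stays in the maintenance population and counts as a maintenance failure, whether or not the device is then removed. Say also how a window cut short by the end of Phase 1 is scored.
3. Reconcile the two section 13.0 sentences (whole treatment duration; 80% of the time from 37 °C) and the section 1.0 population with the steady-state definition, so that one criterion applies throughout, including at the section 6.10 gate.
4. Add a sensitivity analysis whose denominator is all on-device time after first reaching 37.5 °C. This is where a late re-cooled subject would differ (87.5% against 70% in the third assumed case).
5. List each transport with the hours excluded, whether the subject was re-cooled, and whether cold saline was given.

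The cost is a few sentences, one listing and one analysis from the per-second log that already exists. Sample size, treatment and clinical procedures do not change. The downside for the sponsor is that the maintenance rate may be slightly less favourable.

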6.3 Primary Efficacy Endpoint and Success Criteria

This feasibility study should confirm that the COOLSTAT system has the ability to safely and adequately achieve and maintain normothermic cooling therapy with its control system over a specified period for subjects who were enrolled in the study.

This cooling aspect of the trial will be considered a success if at least 75% of the subjects achieve the following criteria:

- Cooling Performance: The subjects reach normothermia (core temperature $\leq 37.5^{\circ}\text{C}$) within 4 hours of starting COOLSTAT cooling.
- Temperature Maintenance: The subjects are held within a 1.5°C temperature band, between $36^{\circ}\text{C} - 37.5^{\circ}\text{C}$, for 80% of the steady state time following the initial achievement of 37.5°C .³

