9.3 Phase 1 – Active Cooling Phase

Subjects will receive COOLSTAT cooling treatment, with a maximum of 30 cmH₂O of air pressure (as automatically controlled by the device). The COOLSTAT will be operated in closed-loop control mode and will automatically modulate and control air flow and maintain the subject's core temperature between 36 °C and 37.5 °C, as measured by the esophageal, SpotOn, or bladder temperature sensor. The device will be set to target 36.5 °C.

The COOLSTAT will attempt to cool to and maintain this temperature range over the phase period. The core temperature will be recorded automatically by the COOLSTAT device, and is displayed on the COOLSTAT screen.

While the COOLSTAT is in use, no other cooling therapies will be used other than antipyretics.

Throughout Phase 1, the subject's temperature and vital signs will be monitored per NCCU protocol, as well as data collected in the CRFs. If any alarms occur, the appropriate action will be taken as described herein. COOLSTAT device errors will be addressed via an available trained technician and study team training (See Operator's Manual for a description of the possible device errors). Treatment may be discontinued at any time if adverse events are encountered or alternate cooling methods are required on an urgent basis. The Investigator or their designee must review any such emergency changes to therapy and complete an Adverse Event form detailing the reason for the change.

Per standard of care in the NCCU, maximum allowed limits will be imposed for a sustained increase in SBP >5 minutes above existing SBP threshold limits (specific to the indication being treated) despite standard of care intervention. In this event, COOLSTAT use will be discontinued for that subject. Once the COOLSTAT is discontinued due to SBP elevation, it will not be restarted for that subject. However, the study team will continue to monitor SBP to see if it recovers back to baseline value after the COOLSTAT is turned off. The Investigator or their designee must complete an Adverse Event form detailing the event and the value of the SBP prior to, during and after the COOLSTAT was used.

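### Cold saline may be given before a transport break in Phase 1, and neither primary criterion has a rule that separates its effect from the device's

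*Combined protocol and SAP*

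**What the plan says.** Section 9.3 contains all the operative rules.

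- On other cooling: "While the COOLSTAT is in use, no other cooling therapies will be used other than antipyretics".
- On transport: "Subjects who are disconnected from the CoolStat for transport may be given a bolus of cold saline before transport". The clinical provider decides case by case.
- On return from transport: "they will be reconnected to the device at steady state if their core temperature" is at or below 37.5°C. Otherwise the device gets up to 4 further hours to reach that level.
- On what is analysed: "Only the total steady state time will be used for analysis".

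The two primary criteria are set in section 6.3 and repeated in sections 13.0 and 13.1. The first begins "Cooling Performance: The subjects reach normothermia (core temperature" and requires 37.5°C or less within 4 hours of starting. The second requires 36 to 37.5°C "for 80% of the steady state time following the initial achievement of" 37.5°C. Section 13.1 sets the target for the first: "The primary hypothesis regarding cooling performance is that at least 75% of the subjects will reach normothermia" in that time. In the section 1.0 summary, maintenance is analysed in the "evaluable population of subjects who achieve normothermia by 4 hours and continue cooling treatment with the COOLSTAT System".

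None of these passages excludes, censors, fails or separately reports a subject who received saline. The case report form does capture the relevant facts: interventions that may affect the core temperature reading (section 1.0), changes to therapy (section 9.3) and medications given (section 9.6). No analysis rule uses those records.

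**The concern.** There is no control arm, so any cooling from another source that the scoring does not identify is credited to the device. Section 6.8 plays down bias because scoring rests on objective temperatures and pre-specified criteria. A temperature-only score, however, cannot tell device cooling from saline cooling.

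The final proportions are compared with 75%. The same criteria also feed section 6.10, where 8 of the first 10 subjects must meet each one before later subjects move from 8 to 24 hours of cooling. A subject wrongly credited to the device could therefore affect both the reported result and the evidence put to the DSMB for longer exposure.

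**Working it through.** **The plan's own figure.** Section 6.6 gives n = 25. With its inputs, [(1.28 × √(0.9 × 0.1) + 0.84 × √(0.75 × 0.25)) / 0.15]² = [(0.384 + 0.364) / 0.15]² = 24.85, rounded up to 25. It reproduces. This point does not turn on it.

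**Following the scoring rules**

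1. *Maintenance.* A subject already normothermic is disconnected, given saline and reconnected at 37.5°C or less. By section 9.3 the subject is at steady state immediately, and the hours that follow enter the 80% calculation with no washout. If first normothermia comes at hour 4, at most 8 − 4 = 4 hours of steady state remain in an 8-hour treatment, so the out-of-band allowance is 0.2 × 4 = 0.8 hours. In a 24-hour treatment it is 0.2 × 20 = 4 hours. A short saline-affected period can therefore matter more in the first 10 subjects.
2. *Cooling performance.* A subject still above 37.5°C is disconnected, given saline and reads 37.5°C or less within 4 hours of start. The criterion in section 6.3 is met, and the subject can also enter the maintenance population. Without that reading, section 9.3 would class the subject as a treatment failure.

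**How much cooling could a bolus supply?** The documents give no volume or saline temperature. Assumed: saline at 4°C, body mass m = 80 kg, specific heats 3.47 (body) and 4.18 (saline) kJ/kg/K, full mixing, 1 L = 1 kg. For start temperature T and volume v:

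drop = 4.18v × (T − 4) / (3.47m + 4.18v)

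Sections 9.1 and 9.2 require a core temperature of at least 38.3°C and below 39.5°C. The required drop therefore runs from 38.3 − 37.5 = 0.8°C to just under 39.5 − 37.5 = 2.0°C.

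| Volume | Drop from 38.3°C | Share of 0.8°C | Drop from 39.4°C | Share of 1.9°C |
|---|---|---|---|---|
| 0.5 L | 0.26°C | 32% | 0.26°C | 14% |
| 1 L | 0.51°C | 64% | 0.53°C | 28% |
| 2 L | 1.00°C | 125% | 1.03°C | 54% |

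Example: 1 L from 38.3°C gives 4.18 × 34.3 / (277.6 + 4.18) = 143.4 / 281.8 = 0.51°C. For 1 L from 38.3°C the drop is 0.58°C at 70 kg and 0.41°C at 100 kg. What matters in practice is the gap left at the time of transport. A subject the device has already brought to 38.0°C has 0.5°C to go, and 1 L supplies 4.18 × 34.0 / 281.8 = 0.50°C.

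**What can one subject do?** Section 13.0 keeps the two airflow groups apart: 20 double-nostril and 10 single-nostril subjects. At the margin, 15/20 = 75% against 14/20 = 70%, and 8/10 against 7/10 at the gate.

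**Illustration for cooling performance, on assumed rates only.** Let the true device success rate be 0.65, and let 10% to 30% of device failures be scored as successes through saline. The scored rate becomes 0.65 + 0.35 × 0.10 = 0.685 up to 0.65 + 0.35 × 0.30 = 0.755. By exact binomial tails:

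- Chance of at least 15 of 20: 25% without saline, 36% to 64% with it.
- Chance of at least 8 of 10: 26% without saline, 34% to 54% with it.

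**The case against.** A reader might infer that section 9.3 contradicts itself. It does not do so literally: the bar covers the time the device is in use, and the bolus is for subjects being disconnected. There is still a tension, because the effect of saline can last into the reconnected period, when the bar applies again.

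A reader might also infer that the reconnection rule itself scores saline cooling under both criteria. In section 1.0 that rule is a footnote to steady state in the maintenance hypothesis, and nothing applies it to cooling performance. The cooling-performance route follows only from the temperature-only definition. It also needs transport before first normothermia, a bolus and a qualifying reading within 4 hours of start.

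Nor do the documents establish that both proportions are biased upward. They give no frequency of transport or saline use and do not say which subjects receive it. A transported subject loses device cooling meanwhile, and an overshoot below 36°C counts against maintenance. On the assumptions above, only the 2 L case covers even the smallest required drop unaided, so success due entirely to saline is not the general case.

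The gate is not automatic either. Section 6.10 also requires the DSMB to review the case report forms and agree, so recorded boluses are open to its scrutiny.

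Finally, failing a subject because a provider gave saline for a necessary transport can bias the result downward. That is a fair objection to using failure scoring as the primary maintenance analysis.

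All of this limits the size and certainty of the problem. It does not supply the missing rule.

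**Conclusion.** The point holds as a gap in scoring. Followed exactly, the plan can credit saline cooling to the device: directly in maintenance, and in cooling performance when transport comes before first normothermia and within the 4 hours. This can inflate the success proportion and the 8-of-10 count.

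The size is unknown. The range of 0.26 to 1.0°C for 0.5 to 2 L rests on assumed saline temperature, body mass, volume and full mixing, and must be set against a required drop of 0.8 to just under 2.0°C. The firm figures are those per subject: 5 points in a group of 20 and 10 points in the first 10. The documents do not support the stronger reading that both primary results are known to be inflated. The rule should be set before the data are analysed, because one subject at the margin can decide either comparison.

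**What to change.** In sections 13.0 and 13.1:

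- **Cooling performance.** Count a success only if 37.5°C or less is reached within 4 hours of start and before any non-antipyretic cooling. Keep as-recorded scoring as a sensitivity analysis.
- **Maintenance.** Keep as-recorded scoring as primary. Add a pre-specified sensitivity analysis that counts subjects given such cooling after first normothermia as not maintained.
- **Reporting.** Give the number of subjects who received such cooling and its timing relative to start, first normothermia and reconnection.
- **Gate.** Show the DSMB the 8-of-10 results under both scorings.

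Separately, the sponsor should reconcile the two statements in section 9.3 on whether and when the bolus is permitted. This review takes no position on that clinical question.

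The cost is analysis-plan wording. The data should already be in the case report form, although it is worth confirming that the time of any bolus is captured. The downside is that the reported success proportion may fall, by up to 5 points per affected subject in a group of 20 and 10 points in the first 10.
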